4.10 HANDLING OF MISSING DATA

Exploration of missing data

The number and percentage of participants with missing data will be reported by study arm at each time point. Baseline characteristics of participants with and without missing data will be tabulated. To explore differential drop-out/withdrawal and trajectories of immunological endpoints by withdrawal status, we will plot antibody titres (Wuhan) over time by strata defined by time of withdrawal (separately by trial group).

Multiple imputation will be performed for the primary analysis of immunological endpoints if more than 5% of participants have missing data. Multiple imputation will be performed using multivariate imputation by chained equations (MICE), with logistic regression for binary variables and linear regression for continuous variables (or predictive mean matching if non-normal). Missing values will be imputed separately by trial arm to ensure treatment effects are maintained, and 50 imputations will be produced. The imputation model will include all variables that are included in the primary analysis model, including stratification variables (age group) and baseline levels of the outcome variable. Covariates considered for inclusion in the imputation model as auxiliary variables include primary series vaccine, duration between different doses and study day of blood draw. Where possible, multiple imputation will be performed simultaneously for all immunological outcomes, but it may be necessary to use separate models at different timepoints due to the timing of analyses. The same imputation models will be used for data set to missing for analyses under the hypothetical strategy. See Estimand-to-Analysis tables under specific outcomes for further detail regarding handling of missing data.

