5 DESCRIPTIVE STATISTICS

5.1 PARTICIPANT DISPOSITION

A CONSORT flow diagram will be used to summarise the study population from screening to analysis, including the number of people who were:

- Screened for eligibility
 - and were eligible at screening
 - and were ineligible at screening (screen failures)*
- Eligible at screening but not randomised*
- Ineligible at screening but randomised (protocol violation)*
- Eligible and randomised (or not randomised for the control group)

[Subsequent numbers will be given by study group]

- Allocated to each study group
 - and received the allocated vaccine
 - and did not receive the allocated vaccine*
- Included in the Reactogenicity and Safety Population (according to vaccine received not allocated)[^]
- Included in the Primary Day-28 Immunology Population[^]
- Included in the Month-6 Immunology Population[^]
- Included in the Month-12 Immunology Population[^]

* Reasons will be provided.

[^]The number of participants with missing data will be noted. Missing data arising from lost-to-follow-up or withdrawal will be enumerated, including the level of withdrawal (from intervention, follow-up, or both, and consent to use data up to the time of withdrawal) and reasons (harms-related reasons for withdrawal will be emphasised).

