Population-level summary measure Geometric mean ratio	Analysis approach Linear regression will be used to estimate the GMR comparing the two vaccine groups, adjusted for the stratifying variable (age group), baseline levels, first booster vaccine and time since first booster. The outcome variable (and the baseline value) will be \log_e transformed before regression, and the GMR (95% CI) will be calculated as the antilogarithms of the mean difference (β_1) and its 95% CI.

[#]Supplementary analyses will be conducted using the Hypothetical Strategy for handling intercurrent events (see Table 14).

Table 7. Estimand-to-Analysis⁵ table for at least one solicited grade 3 or 4 local or systemic reaction within 7 days of boosting (primary reactogenicity endpoint)

Primary Objective (as per Protocol): Assess the rate and severity of reactogenicity within one-week post-second booster for the Moderna and Novavax groups (Timepoint – daily, for seven days post-vaccination).	
Estimand:	Incidence risk of a grade 3 or 4 local or systemic reaction within 7 days (inclusive) of boosting, by vaccine group in adults 18 years or older who have received their third dose of COVID-19 vaccine at least six months previously
ESTIMAND Attributes:	Incorporation of Estimand Attribute in ANALYSIS:
Treatment Bivalent mRNA Moderna COVID-19 vaccine and protein-based Novavax COVID-19 vaccine	Study arms Bivalent Moderna vaccine arm (Moderna BA.1 and Moderna BA.4-5 groups combined) Novavax vaccine arm
Target population Adults 18 years or older who have received their third dose of COVID-19 vaccine at least six months previously	Analysis set (“Reactogenicity Population”) All participants, as per trial vaccine received (regardless of allocation).
Variable Grade 3 or 4 local or systemic reaction within 7 days (inclusive) of boosting.	Outcome measure Presence of at least one solicited grade 3 or 4 local or systemic reaction within 7 days (inclusive) of boosting.
Handling of intercurrent events	
Event (up to and including Day-7)	Strategy⁴
SARS-CoV-2 infection	While Negative (values up to the day of the first positive test are used)
Death	While Alive (values up to the time of death are used)

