Population-level summary measure Incidence risk (proportion) of at least one solicited grade 3 or 4 local or systemic reaction within 7 days (inclusive) of boosting.	Handling of missing data It will be assumed that participants with missing reactogenicity datapoints (collected daily for each reaction type) did not experience the specific reaction on the day/s where the value is missing. Missing data by day and reaction will be described by study group. Analysis approach Proportions will be estimated with 95% Clopper-Pearson binomial confidence intervals using the ci Stata command. Supplementary analysis: The following reaction-specific descriptive analyses will also be conducted: 
Number and percentage of individuals with each reaction type, presented in a radial graph (Dummy Figure 2).Number and percentage of participants with each reaction type, by severity grade (Dummy Figure S 1).Distribution of the day of onset for each reaction typeDistribution of the duration of each reaction type

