8.2 ANALYSIS OF SECONDARY SAFETY ENDPOINTS

Table 11 specifies the secondary safety endpoints, including the timepoint measured, population measure, groups being compared and the measure of association between groups (where relevant).

Table 11. Safety endpoints

Safety Endpoint	Outcome	Timepoint	Population measure	Comparison	Measure of association
i.	Any [#] AE to Day 28 (inclusive)*	28 days post-booster	Frequency [N (%)]	Group A vs Group B	Descriptive only
ii.	Any [#] AE to Day 28 (inclusive)* [^] by severity	28 days post-booster	Frequency [N (%)]	Group A vs Group B	Descriptive only
iii.	Any [#] AE to Day 28 (inclusive)* [^] by causality assessment	28 days post-booster	Frequency [N (%)]	Group A vs Group B	Descriptive only
iv.	Any AE to Day 28 (inclusive)* by SOC and severity [^]	28 days post-booster	Frequency [N (%)]	Group A vs Group B	Descriptive only
v.	Duration [#] of AE to Day 28 (inclusive)* by SOC [^]	28 days post-booster	Median days {25 th – 75 th percentile}, min - max	Group A vs Group B	Descriptive only
vi.	Day of AE onset (days post-booster) to Day 28 (inclusive)* by SOC [^]	28 days post-booster	N by Day	Group A vs Group B	Descriptive only
vii.	AE to Day 28 (inclusive)* by Outcome ^{**^}	28 days post-booster	Frequency [N (%)]	Group A vs Group B	Descriptive only
viii.	Medically attended unsolicited AE to Month-3 visit (inclusive)	90 days post-booster	Frequency [N (%)]	Group A vs Group B	Descriptive only
ix.	SAE to study-end by SOC and expectedness [^]	Month-12 visit	Frequency [N (%)]	Group A vs Group B	Descriptive only
x.	SAE to study-end by Outcome ^{**^}	Month-12 visit	Frequency [N (%)]	Group A vs Group B	Descriptive only

[#]The Safety analysis will only include unsolicited adverse events; solicited adverse events are considered in the Reactogenicity analysis. *Adverse events within 28 days inclusive will be considered, rather than all adverse events before the Day-28 visit, which can occur between 28- and 35-days post-booster. **Outcome categories are Resolved, Resolved with sequelae, Ongoing, Fatal and Unknown; denominator is the total number of SAEs rather than the number of participants. [^]Recurrent events in the same individual will be counted as a single event (using information from the most severe occurrence); all recurrences will be included in the line list of all adverse events. [#] The duration of 'Ongoing' adverse events will be the number of days between the onset and the last visit.

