9.4 SUPPLEMENTARY AND SENSITIVITY ANALYSES

The following supplementary and sensitivity analyses will be conducted. The supplementary analyses use alternative strategies for handling intercurrent events and thus target different estimands; the results will help to fully understand the impact of the intercurrent events and the strategies used to handle them. The sensitivity analyses target the same estimands and test the sensitivity of deviations from assumptions about missing data.⁴

Table 14. Supplementary and Sensitivity Analyses

Endpoints	MAIN ANALYSIS (Complete Case)		SUPPLEMENTARY ANALYSIS (for IcE Strategy)		SENSITIVITY ANALYSIS (for >5% missingness)
	Estimand	IcE & Strategy	Change to Estimand from Main Analysis	IcE & Strategy	
Primary immunological endpoint (seroresponse at Day-28)	Geometric mean ratio (GMR) of binding antibodies (IgG ELISA – Wuhan, Omicron BA.1 and Omicron BA.4/5) 28 days post-vaccination comparing the two vaccine groups (bivalent Moderna and Novavax) in adults 18 years or older who have received their third dose of COVID-19 vaccine at least six months previously, irrespective of SARS-CoV-2 infection.	SARS-CoV-2 infection: Treatment Policy	..., irrespective of SARS-CoV-2 infection ≤ 14 days post-booster, and in a hypothetical scenario in which there were no breakthrough infections on or after Day 15.	SARS-CoV-2 infection ≤ 14 days post-booster: Treatment Policy	Imagines a scenario in which breakthrough infections on or after Day 15 did not occur.
Day-28 Secondary immunological endpoints[#]	[Geometric mean ratio in [OUTCOME] OR Difference in Means of [OUTCOME]] [#] 28 days post-vaccination comparing the two vaccine groups (bivalent Moderna and Novavax), in adults 18 years or older who have received their third dose of COVID-19 vaccine at least six months previously, irrespective of SARS-CoV-2 infection.	SARS-CoV-2 infection: Treatment Policy	As above	As above	As above
Month-[6/12/18/24/30][#] Secondary immunological endpoints[#]	[Geometric mean ratio in [OUTCOME] OR Difference in Means of [OUTCOME]] [#] [6/12] [#] months post-vaccination comparing the two vaccine groups (bivalent Moderna and Novavax), in	SARS-CoV-2 infection: Treatment Policy	..., irrespective of SARS-CoV-2 infection ≤ 14 days post-booster or receipt of a 5 th dose (self-initiated), and in a	SARS-CoV-2 infection ≤ 14 days post-booster:	As above

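### Primary reactogenicity risk: a vaccinated participant with no diary data is scored as having had no grade 3 or 4 reaction, and no planned analysis tests that assumption

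*SAP*

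**What the plan says.** SAP Section 7.2, Table 7, defines the outcome as at least one solicited grade 3 or 4 local or systemic reaction within 7 days of boosting. The analysis set is "All participants, as per trial vaccine received (regardless of allocation", with no minimum amount of diary data. For missing values, it assumes that anyone who has "missing reactogenicity datapoints (collected daily for each reaction type) did not experience the specific reaction on the day/s where the value is missing". The risk in each arm is a proportion with a 95% Clopper-Pearson interval, and Table 5 marks the endpoint as descriptive.

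The SAP does plan to report missingness. Table 7 states: "Missing data by day and reaction will be described by study group". Section 4.10 adds: "Baseline characteristics of participants with and without missing data will be tabulated". The footnote to the participant flow in Section 5.1, which covers the Reactogenicity and Safety Population, says: "The number of participants with missing data will be noted".

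Alternative analyses for missing data are planned only for the immunological endpoints. Section 4.10 reads: "Multiple imputation will be performed for the primary analysis of immunological endpoints if more than 5% of participants have missing data". Section 9.4 says of its sensitivity analyses: "The sensitivity analyses target the same estimands and test the sensitivity of deviations from assumptions about missing data". Every row of Table 14 is an immunological endpoint.

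**The concern.** The rule is written per day and per reaction, where a single blank may be harmless. Combined with an analysis set of everyone vaccinated, it also decides the case of a participant with no data: no reaction on all seven days, at full weight in the denominator. The SAP does not mention that case.

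This is one of the two primary endpoints, and it measures tolerability, where understatement is the unfavourable direction. Because the endpoint is descriptive, the percentage and its interval are the main result. The planned summaries will show how much is missing but not how far the result depends on the no-reaction assumption. As worded, they need not separate a participant with nothing recorded from one with a single blank entry. If missingness differs between arms, the descriptive contrast shifts as well.

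**Working it through.** **The plan's own figure.** The reactogenicity precision statement (SAP 3.5, Protocol 11.1) reproduces: 1.96 × √(0.5 × 0.5 / 100) = 0.098, or 9.8 points. The Clopper-Pearson interval named for the analysis gives 39.8% to 60.2% for 50/100, about 10.2 points each side. Neither allows for missing diary data.

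**Direction.** Each participant's outcome is the maximum of the day-by-reaction indicators. Replacing an unknown 0 or 1 by 0 can leave that maximum as it is or lower it. The denominator is fixed, so the estimate is at or below its complete-diary value. It is unchanged if a grade 3 or 4 reaction is recorded on another day, or if those without data had no such reaction.

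**Does another analysis cover it?**
- Section 4.10 imputation: immunological endpoints only.
- Table 14: no reactogenicity row.
- Table 7 supplementary analyses: reaction type, grade, onset and duration, all under the same rule.
- Table 11 safety analysis: "The Safety analysis will only include unsolicited adverse events; solicited adverse events are considered in the Reactogenicity analysis".
- Protocol 11.3.1: no other rule for missing diary data.

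**Size.** The arm size of 225 is from SAP 3.5. The true risk p and the fraction f with no data are assumed. With equal risk in those with and without data, expected estimate = p × (1 − f):
- p = 20%: 0.20 × 0.98 = 19.6%; 0.20 × 0.95 = 19.0%; 0.20 × 0.90 = 18.0%.
- p = 5%: 0.05 × 0.98 = 4.9%; 0.05 × 0.95 = 4.75%; 0.05 × 0.90 = 4.5%.
- Unequal missingness: a 10% risk in both arms, with f = 2% in one and 10% in the other, reads as 9.8% and 9.0%.

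Examples for one arm of 225 with x observed events and m participants without data (95% Clopper-Pearson intervals in brackets):

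| m | x | Current rule x/225 | With data x/(225 − m) | Upper bound (x + m)/225 |
|---|---|---|---|---|
| 5 | 44 | 19.6% (14.6–25.3) | 20.0% (14.9–25.9) | 21.8% (16.6–27.7) |
| 11 | 43 | 19.1% (14.2–24.9) | 20.1% (14.9–26.1) | 24.0% (18.6–30.1) |
| 22 | 41 | 18.2% (13.4–23.9) | 20.2% (14.9–26.4) | 28.0% (22.2–34.4) |
| 11 | 11 | 4.9% (2.5–8.6) | 5.1% (2.6–9.0) | 9.8% (6.2–14.4) |

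In every row the with-data value lies inside the current-rule interval. The upper bound assumes an event in every participant without data.

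Exact coverage of the true risk by the nominal 95% interval, with the event count distributed as Binomial(225, p(1 − f)):

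| True risk | f = 0 | 2% | 5% | 10% | 20% |
|---|---|---|---|---|---|
| 5% | 97.0 | 97.1 | 97.2 | 96.9 | 94.6 |
| 15% | 95.9 | 95.7 | 94.6 | 91.1 | 75.9 |
| 20% | 95.5 | 95.2 | 93.8 | 88.7 | 66.9 |

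**Why not a bound for every blank cell.** SAP Table 4 lists 14 graded reactions, so a diary has 14 × 7 = 98 graded cells. With 1% independent blanks, 1 − 0.99^98 = 62.7% of diaries have at least one blank cell, and a cell-level worst case would say nothing useful. With 1% of whole days blank, 1 − 0.99^7 = 6.8% of diaries are affected.

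**The case against.** The best defence is that little will be missing. Solicited events are documented at the Day 1 and Day 7 calls (Protocol 7.1 to 7.2.3), and at Day 7 paper-card details are read out or photographed, so an unreturned card need not mean no data. The Day 28 visit collects cards and updates solicited events. Primary-outcome data are monitored at 100% (Protocol 10.2), missing data are queried (10.3), and graded reactions must be cleaned and locked before the Day-28 analysis (SAP 4.8 and 4.9). This stands as a reason to expect a small effect. It sets no ceiling on missingness and supplies no estimate under another assumption.

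The rule is also openly stated as an assumption, and missingness will be reported. A reader could take the smallest day-by-reaction missing count as a ceiling on the number with no data and work out limits from it. That is fair, but it is neither a planned estimate nor the exact number.

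The immunological endpoints get a missing-data analysis only above 5% missing, so unconditional rows here ask for more. That is true, but Table 7 has no threshold and no alternative at any level of missingness.

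Finally, the proposed rows leave the per-day assumption untested in partly completed diaries, and the upper bound is extreme. Both are real limits and should be stated with the results.

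**Conclusion.** The concern holds. Table 7 makes a participant with no reactogenicity data a full-weight non-event, the resulting error can only be downward relative to complete diaries, and nothing planned varies the assumption.

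Its likely size is modest. With 5% or fewer lacking data, equal risk in those with and without data, and a true risk up to 20%, the understatement is at most about 1 point and coverage stays at 93.8% or above in the cases worked. Coverage falls clearly only at higher fractions (75.9% for a 15% risk with 20% lacking data), and nothing in the documents suggests missingness on that scale. If those without data had more reactions than the others, the understatement would be larger, up to the bounds shown. If they had none, it would be zero. This is an inexpensive improvement that should be made, not a flaw that undermines the endpoint.

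**What to change.** Add to SAP Tables 7 and 14, for each arm:

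- **(a)** the proportion among vaccinated participants with at least one completed diary day or a completed Day-7 symptom review, scored on the worst observed grade;
- **(b)** an upper bound with all vaccinated participants in the denominator, counting as events only those with no reactogenicity data at all, with their number stated.

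Days after a positive test or death, already excluded by the While Negative and While Alive strategies, should not count as missing. If a bound for partial diaries is also wanted, define incomplete in advance, for example as no entries on one or more whole days, so that one blank cell does not trigger it.

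Timing matters because SAP 1.2 says an SAP dated 19/3/2024 covered data to Day 28, and the documents do not say whether reactogenicity has been analysed. Make (a) the main analysis only if it has not. Otherwise keep the current main analysis and label (a) and (b) as sensitivity analyses.

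The cost is one SAP paragraph and two rows per arm, with no new data. Row (a) has a slightly wider interval: with 11 of 225 lacking data, 14.9–26.1% on 214 participants against 14.2–24.9% on 225. It can still be biased if missingness is related to reactions, and (b) does not cover reactions missed in partial diaries.

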8 ANALYSIS OF THE SECONDARY OUTCOMES

8.1 ANALYSIS OF SECONDARY IMMUNOLOGICAL ENDPOINTS

Table 8 lists the secondary immunological endpoints, including the timepoint measured, population measure, groups being compared and the measure of association between groups. Note there may be additional secondary immunological outcome variables (e.g. relating to new variants of concern) that become available after this SAP is written. These additional variables will be analysed in the same way as other secondary immunological variables listed in Table 8, with analysis dependent on the distribution (e.g. whether symmetrical).

Table 8. Secondary immunological endpoints

Outcome	Population measure	Measure of association	Timepoint	Comparisons
Binding antibody				
Binding antibody (IgG) (Wuhan) BAU/ml	GM (95% CI)	GMR (95% CI)	Month-6	Group A vs B, Group A vs control, Group B vs control
			Month-12	Group A vs B, Group A vs control, Group B vs control
			Month-18	Group A vs B, Group A vs control, Group B vs control
			Month-24	Group A vs B, Group A vs control, Group B vs control
			Month-30	Group A vs B, Group A vs control, Group B vs control
Binding antibody (IgG) (Omicron BA.1), RU/ml	GM (95% CI)	GMR (95% CI)	Day-28	Group A vs B
			Month-6	Group A vs B, Group A vs control, Group B vs control
			Month-12	Group A vs B, Group A vs control, Group B vs control
			Month-18	Group A vs B, Group A vs control, Group B vs control
			Month-24	Group A vs B, Group A vs control, Group B vs control
			Month-30	Group A vs B, Group A vs control, Group B vs control
Binding antibody (IgG) (Omicron BA.4/5), EU/ml	GM (95% CI)	GMR (95% CI)	Day-28	Group A vs B
			Month-6	Group A vs B, Group A vs control, Group B vs control
			Month-12	Group A vs B, Group A vs control, Group B vs control
			Month-18	Group A vs B, Group A vs control, Group B vs control
			Month-24	Group A vs B, Group A vs control, Group B vs control
			Month-30	Group A vs B, Group A vs control, Group B vs control
Binding antibody (IgG) (Omicron JN.1), EU/ml	GM (95% CI)	GMR (95% CI)	Day-28	Group A vs B
			Month-6	Group A vs B, Group A vs control, Group B vs control
			Month-12	Group A vs B, Group A vs control, Group B vs control
			Month-18	Group A vs B, Group A vs control, Group B vs control
			Month-24	Group A vs B, Group A vs control, Group B vs control
			Month-30	Group A vs B, Group A vs control, Group B vs control
Functional antibody				
Functional antibody sVNT (Wuhan), U/ml	GM (95% CI)	GMR (95% CI)	Day-28	Group A vs B
			Month-6	Group A vs B, Group A vs control, Group B vs control
			Month-12	Group A vs B, Group A vs control, Group B vs control
			Month-18	Group A vs B, Group A vs control, Group B vs control
			Month-24	Group A vs B, Group A vs control, Group B vs control
			Month-30	Group A vs B, Group A vs control, Group B vs control
Functional antibody sVNT (Omicron BA.1), U/ml	GM (95% CI)	GMR (95% CI)	Day-28	Group A vs B
			Month-6	Group A vs B, Group A vs control, Group B vs control
			Month-12	Group A vs B, Group A vs control, Group B vs control
			Month-18	Group A vs B, Group A vs control, Group B vs control
			Month-24	Group A vs B, Group A vs control, Group B vs control
			Month-30	Group A vs B, Group A vs control, Group B vs control
Functional antibody sVNT (Omicron BA.4/5), U/ml	GM (95% CI)	GMR (95% CI)	Day-28	Group A vs B
			Month-6	Group A vs B, Group A vs control, Group B vs control
			Month-12	Group A vs B, Group A vs control, Group B vs control
			Month-18	Group A vs B, Group A vs control, Group B vs control
			Month-24	Group A vs B, Group A vs control, Group B vs control
			Month-30	Group A vs B, Group A vs control, Group B vs control
Neutralising antibody				
Neutralising antibody (Wuhan), NT50	GM (95% CI)	GMR (95% CI)	Day-28	Group A vs B
			Month-6	Group A vs B, Group A vs control, Group B vs control
			Month-12	Group A vs B, Group A vs control, Group B vs control

Neutralising antibody (variant of concern) #, NT50	GM (95% CI)	GMR (95% CI)	Day-28	Group A vs B
			Month-6	Group A vs B, Group A vs control, Group B vs control
			Month-12	Group A vs B, Group A vs control, Group B vs control
Cellular mediated immunity				
Ag1 IFN γ (IU/ml)	GM (95% CI) or median (95% CI) [^]	GMR (95% CI) or difference in medians (95% CI) [^]	Day-28	Group A vs B
			Month-6	Group A vs B, Group A vs control, Group B vs control
			Month-12	Group A vs B, Group A vs control, Group B vs control
Ag2 IFN γ (IU/ml)	GM (95% CI) or median (95% CI) [^]	GMR (95% CI) (95% CI) [^]	Day-28	Group A vs B
			Month-6	Group A vs B, Group A vs control, Group B vs control
			Month-12	Group A vs B, Group A vs control, Group B vs control

GM: Geometric mean. GMR: Geometric mean ratio

#variants of concern for neutralising antibody to be confirmed

[^]Data will summarised using medians, and compared across groups using difference in medians in the case of negative and zero values and log-transformation not possible

